### **B.6.2. PRE-SCREENING/CONSENT/ENROLLMENT**

[figure not shown]
Medical records of all subjects deemed by the Investigator to be potential candidates for the study will be de-identified and sent to a sponsor designated physician for pre-screening. De-identified medical records should include detailed medical and surgical history of the pain condition under study as well any information about comorbidities. Any imaging studies (such as MRI, CT, X-ray) should be included for evaluation of the study candidate. Once the site has received confirmation that subject may be an appropriate candidate for this study, the site may proceed with the eligibility process. This de-identified pre-screening process assists in reducing unnecessary visits for subjects that would not be eligible for this study.

Written informed consent for participation in the study must be obtained from subjects

before initiation of any study-related activities, including those that assess eligibility. Following informed consent, subjects will be assigned a unique subject identification number and will be considered to be enrolled in the study. Eligibility for advancing to the next stage of the study will be evaluated by the site Investigator based on the defined inclusion and exclusion criteria. Subjects will be assessed for pain intensity and disability.

### **B.6.3. ELIGIBILITY CRITERIA EVALUATION**

The eligibility of subjects who have consented participation will be assessed based on the inclusion and exclusion criteria. Study subjects must meet all of the study inclusion criteria and none of the study exclusion criteria to be eligible. Assessments for eligibility include average pain intensity (which will be used as Baseline pain intensity), other pain intensity (such as secondary pain or related pain), medication usage, medical records and history, and the Investigator's clinical judgment. Subjects with confirmed eligibility will proceed to Baseline assessment, while subjects who do not will be considered screen failures and discontinued from the study.

**Figure 1.** A flowchart of the study.

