### **B.3.2. INCLUSION CRITERIA**

In order to participate in the study, a subject must **MEET ALL** of the following inclusion criteria:

1. Be diagnosed with chronic, intractable pain of the upper limbs related to the cervical spine and/or neuropathic arm pain.
2. Be a candidate for SCS system (trial and implant) per labeled indication (upper limb pain due to one of the conditions listed in indications statement)
3. Considering daily activity and rest, has average upper limb pain intensity of  $\geq 5$  out of 10 cm on the Visual Analog Scale (VAS) at enrollment
4. Be willing and capable of giving written informed consent to participate in this clinical study based on voluntary agreement after a thorough explanation of the subject's participation has been provided.
5. Be willing and capable of subjective evaluation, read and understand written questionnaires, and read, understand and sign the written informed consent.
6. Be 18 years of age or older at the time of enrollment
7. Be on a stable pain medication regime, as determined by the study Investigator, for at least 30 days prior to enrolling in this study
8. Be willing and able to comply with study-related requirements, procedures, and visits, including not increasing pain medications through the three months visit
9. Has adequate cognitive ability to use a patient programmer and recharger as determined by the Investigator

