#### **B.6.1. SUMMARY OF STUDY PROTOCOL**

Potential study subjects will be identified from a pool of candidates for SCS therapy that are either affiliated with or referred to the clinical sites. Advertisements of the study may be used for recruitment purposes, upon approval of the patient recruitment materials by the study IRB(s). An informed consent form (ICF) will be given to the potential subject for private evaluation. The Investigator or Study Clinical Staff will be available to respond to

any questions the potential subject may have during evaluation of the ICF. Potential study subjects willing to participate in the study will visit the study site for providing written consent and for evaluation of eligibility to participate based on inclusion and exclusion criteria. Once a consented subject is deemed qualified to participate in the study, baseline assessments will occur followed by scheduling of the trial stimulation phase.

Subjects who complete a successful DTM SCS trial phase will be scheduled to receive a permanent implant of the SCS system and will undergo 3 months of therapy with assessments at 1, 3, 6 and 12 months after the activation of the implanted device. All current subjects or those who have completed their 6-month visit will be offered to return for an additional 12-month visit. This would increase their commitment to the study to 14 months. Baseline assessments will include measures for pain intensity, use of medication, and extent of disability.

Subjects will undergo a Trial Phase lasting up to 10 days to determine subject's response to DTM SCS. Commercially available stimulation leads and a commercially available external neurostimulator (ENS) will be used during the Trial Phase. Subjects will evaluate DTM SCS therapy based on pain intensity under optimal stimulation parameters within the specifications of the device. Subjects who have a "successful Trial Phase" (defined as a 40% or greater pain reduction from Baseline in their upper limb pain) will proceed to permanent implantation of a SCS system.

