#### **B.6.4. BASELINE**

A subject that is eligible to continue into the trial phase according to the inclusion and exclusion criteria will be requested to fill out standard questionnaires that will assess extent of disability and use of medications. The medical and surgical history of the subject will also be collected. At this visit and subsequent visits, the subject will be assessed for study-related adverse events, medication usage and will be reminded to not increase pain medications from baseline through the 3-Month Visit. Pre-operative assessments will follow the standard of care for SCS therapy and be determined by the site Investigator.

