### **B.6.6. END OF TRIAL ASSESSMENT**

At the end of the Trial Phase, subjects will be assessed for pain intensity under optimal therapy parameters. Anterior-posterior (AP) and lateral X-ray imaging may be done at the end of the Trial Phase. The subject will be assessed for study-related adverse events and medication usage.

Subjects who have a "successful Trial Phase" (defined as a 40% or greater pain reduction from Baseline in the upper limbs pain and the subject would like to move forward to the implant phase) will proceed to permanent implantation of a SCS system to evaluate DTM SCS programming. Permanent implantation of the Intellis™ SCS system will be scheduled. A threshold of 40% for the Trial Phase was predetermined as the minimum pain reduction that warrants consideration of a permanent implant and an opportunity to achieve a 50% pain reduction as defined in the Individual Subject Success criterion (see Section B.7.3).

Subjects who did not achieve 40% or greater pain reduction in upper limb and do not receive permanent implantation will exit the study after being followed up for two weeks after removal of the leads to assess study-related adverse events.

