## **B.8. EVALUATION CRITERIA**

### **B.8.1. EFFECTIVENESS**

Results of the tests and standard questionnaires will be recorded in Case Report Forms at Baseline and during follow-up visits. Changes from Baseline will be calculated.

Effectiveness will be measured for each subject using the following tests:

- Pain
- Visual Analog Scale (VAS, 10 cm) at Baseline, End of Trial Phase, Months 1, 3, 6 and12 monthsDisability
  - Pain Disability Questionnaire at 3, 6 and 12 months
- Impression of Change in Quality of Life
  - Patient Global Impression of Change at 3, 6 and 12 months
- Satisfaction with Therapy
  - Subject Satisfaction Questionnaire at 3, 6 and 12 months
- Paresthesia generated by the stimulation
  - Paresthesia Questionnaire at 3, 6 and 12 months

Study personnel will be appropriately trained for administration of each test.

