**Table 1. Schedule of Study Activities**

Activity	Pre-Trial Phase		Trial Phase		Permanent Phase					12 months visit (±31 days after activation)
	Enrollment	Baseline	Start Trial Phase	End Trial Phase (up to 10 days after trial starts)	Permanent Implant (up to 60 days after end of trial)	Device Activation (0-14 days after implant)	1-month visit (±15 days after activation)	3 months visit (±21 days after activation)	6 months visit (±31 days after activation)	
Informed Consent	X									X b)
Pain Intensity Evaluation (VAS)	X			X			X	X	X	X
Medication Use	X	X	X	X	X	X	X	X	X	X
Medical/Surgical History	X	X								
Eligibility Criteria Evaluation	X									
Pain Disability Questionnaire		X							X	X
AP/Lateral x-ray imaging			X	[X]	X	[X]	[X]	X	[X]	[X]
Paresthesia Questionnaire								X	X	X
Patient Global Impression of Change								X	X	X
Subject Satisfaction								X	X	X
Adverse Event Monitoring		X	X	X	X	X	X	X	X	X
Device Programming			X			X	[X]	[X]	[X]	[X]
Device Programming Log				[X]			[X]	[X]	[X]	[X]
Study Completion				X a)				[X] c	[X] c	X c

[X] Optional activity.

a) For subjects that do not have a successful Trial Phase.

b) Some subjects may need to be reconsented to complete these visits.

c) Some subjects were originally consented to complete the study at the 3 or 6 month visit and may not consent for additional visit.

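### One enrollment VAS qualifies subjects and then serves as Baseline for the 40% trial-success threshold and both pain endpoints, so reported relief is more favourable than with an independent baseline reading

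*Combined protocol and SAP*

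**What the plan says.** - **Entry.** Section B.3.2, criterion 3: "Considering daily activity and rest, has average upper limb pain intensity of" at least 5 out of 10 cm, measured at enrollment.
- **Baseline.** Section B.6.3 lists the eligibility assessments and includes "average pain intensity (which will be used as Baseline pain intensity".
- **Schedule.** In Table 1 the row "Pain Intensity Evaluation (VAS" is marked at Enrollment, blank at Baseline, and next marked at End Trial Phase. Section B.6.4 has subjects at the Baseline visit "fill out standard questionnaires that will assess extent of disability and use of medications"; it lists no pain score.
- **Implant decision.** A successful trial is "defined as a 40% or greater pain reduction from Baseline in their upper limb pain" (B.6.1, repeated in B.6.6).
- **Endpoints.** The responder rule in B.7.3 (a fall of 50% or more at 3 months) and the mean VAS change in B.7.4 are both taken from Baseline. The primary endpoint counts implanted subjects only.
- **Design and analysis.** The study is single-arm and open-label (B.5.3). The analysis is descriptive, with no formal hypothesis (B.9.2).

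Two sentences mention pain at Baseline: "Baseline assessments will include measures for pain intensity, use of medication, and extent of disability" (B.6.1) and "Visual Analog Scale (VAS, 10 cm) at Baseline, End of Trial Phase" (B.8.1). Neither provides a second reading that would replace the one named in B.6.3.

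**The concern.** A VAS reading is the subject's underlying pain plus error. Requiring 5 cm or more favours readings whose error was positive. Requiring a 40% fall from the same reading favours them again, because a higher starting score makes the fall easier to reach. The primary endpoint is then computed only in subjects who passed both steps, and it divides by that same reading.

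The responder rate and the mean change are therefore both pushed in the therapy's favour, relative to a baseline whose error played no part in selection. A larger sample would not reduce this. Without a control arm, the comparison with baseline cannot reveal it. Section B.5.2 says the plan was designed to minimise bias but names no measure against this one.

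**Working it through.** **1. The plan's own figures.** There is nothing to reproduce. The 45 implanted subjects (B.5.4.1) rest on no SD, precision target or hypothesis. Only ratios follow: 55/90 = 61% trialed and 45/55 = 82% implanted. Every VAS input below is an assumption.

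**2. Mechanism in one subject.** Take true pain 6.5 cm and an enrollment error of +1.5 cm, so the recorded score is 8.0.
- The 40% threshold is met at 0.6 × 8.0 = 4.8 cm instead of 0.6 × 6.5 = 3.9 cm.
- The responder rule is met at 0.5 × 8.0 = 4.0 cm instead of 0.5 × 6.5 = 3.25 cm.

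**3. The 5 cm cut alone.** For normal scores, the expected overstatement of baseline is (1 − reliability) × SD × φ(a)/(1 − Φ(a)), with a = (5 − mean)/SD and SD that of the observed score. For mean 6.5, SD 2.0 and reliability 0.5: a = −0.75, φ = 0.3011, 1 − Φ = 0.7734, and 0.5 × 2.0 × 0.3011/0.7734 = 0.39 cm.

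| Mean, SD (cm) | Reliability 0.5 | 0.7 | 0.9 |
|---|---|---|---|
| 5.5, 2.0 | 0.65 | 0.39 | 0.13 |
| 6.5, 2.0 | 0.39 | 0.23 | 0.08 |
| 7.0, 1.5 | 0.14 | 0.08 | 0.03 |

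**4. Cut and 40% threshold together, by simulation.** Let T be true pain (mean 6.5 to 7.0, between-subject SD 1.2 to 1.5) and R relief (mean 55%, SD 20 to 25%). Readings carry independent errors with SD 0.8 to 1.5.
- Enrollment = T + e1; end of trial = T(1 − R) + e2; 3 months = T(1 − R) + e3; independent baseline = T + e4.
- Implanted: enrollment ≥ 5 and end of trial ≤ 0.6 × enrollment.
- Responder: 3 months ≤ 0.5 × the reference score.

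Among implanted subjects the enrollment score is 0.16 to 0.63 cm too high. This passes one for one into the mean change, which is the 3-month score minus Baseline. With the 40% threshold kept on the enrollment score, the responder rate is 2.3 to 6.4 points higher using enrollment than using the independent reading. At the upper end (mean 6.5, between-subject SD 1.2, error SD 1.5, relief SD 20%) it is 69.9% against 63.5%.

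**5. What other choices of reference achieve.**
- Mean of the two readings as reference, threshold on enrollment: the rate falls by only 0.8 to 2.8 points. In the same example it goes from 69.9% to 67.1%, which removes 2.8 of the 6.4 points.
- Second reading for both the threshold and the responder rule: the rate falls by about 0.4 to 2.4 points, because the threshold now selects on the error of the second reading.

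**6. Wider assumptions.** With mean 5.5 to 7.0, observed SD 1.5 to 2.0, reliability 0.5 to 0.9 and mean relief 40% or 55% (SD 25%), the step 4 comparison gives about 1 to 10 points. The worst case is 62.0% against 52.5%. With no true effect at all, 0% to 14% of subjects passing the threshold count as responders. With a separate baseline for both rules it is 0% to 9%. Reuse alone cannot produce a high responder rate.

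**7. Scale.** Among 45 subjects, 0.023 × 45 = 1.0 and 0.064 × 45 = 2.9, so one to three subjects. The exact 95% interval for 27/45 (60%) is 44.3% to 74.3%.

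**The case against.** **Size.** The upper end needs noisy scores: between-subject SD 1.2 with error SD 1.5 is a reliability of 1.44/(1.44 + 2.25) = 0.39. The item asks for average pain over activity and rest, and medication must have been stable for 30 days, so error may be smaller. With error SD 0.8 the 5 cm cut alone moves baseline by only about 0.1 cm. This stands as a reason to present a range. It does not remove the effect, since one averaged item is still one reading.

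**Consequence.** There is no test or success threshold, and the shift is smaller than sampling error. Both are true. But the responder rate is then the study's main product, and an interval around it neither shows nor corrects a one-directional shift.

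**True relief.** A reader might infer that the reported rate exceeds the share of subjects with real relief of 50% or more. The documents do not support that. In the step 4 scenarios that true share among implanted subjects is 72% to 78%, against 70% to 77% observed with the reused score; error in the 3-month reading also misclassifies true responders. At an assumed mean relief of 30% to 40% the observed rate is mostly above the true share. The comparison turns on inputs the plan does not give.

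**A missing reading.** A reader might also take B.8.1 and Table 1 as contradictory about a Baseline VAS. Section B.6.3 settles this: the enrollment reading is the Baseline reading.

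**Timing.** The plan was first released on 20APR2020 and this revision is dated 30JUL2021. Table 1, footnote c, refers to subjects originally consented to finish at 3 or 6 months. A new reading would cover only later subjects. This stands and limits what the change can achieve.

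**Conclusion.** The concern holds as a modest bias built into the design. One enrollment reading, selected at 5 cm and again by the 40% threshold, is the reference for the primary responder rate and the mean VAS change. Both come out more favourable than with an independent baseline: about 0.2 to 0.6 cm on baseline and about 2 to 6 points on the responder rate. These sizes rest on the assumed inputs in step 4, on errors that are independent between readings, and on the 40% threshold staying on the enrollment score. They should not be quoted for averaging the two readings or for moving the threshold to the second one.

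The finding is relative to an independent reading, not to true relief. It concerns a descriptive estimate, not an error rate. Placebo response and natural history stay uncontrolled under any definition of baseline.

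**What to change.** 1. In Table 1 and B.6.4, add an upper limb VAS at the Baseline visit. If enrollment and Baseline fall on the same day, take it before the procedure at Start Trial Phase.
2. Leave eligibility and the 40% threshold on the enrollment VAS, exactly as now. Both are worded from Baseline or feed it, so name the enrollment score explicitly in B.6.1, B.6.5 and B.6.6; otherwise redefining Baseline would silently move the implant decision.
3. Amend B.6.3, B.7.3 and B.7.4 so that the second VAS alone, not the mean of the two, is the denominator of the responder rate and the reference for the mean VAS change. Align B.6.1, B.7.5 and B.8.1 with this.
4. For subjects already past that visit, keep the enrollment-based result and label it. Report both versions wherever both scores exist.
5. State regression to the mean as a limitation when reporting. If no subjects remain to be enrolled, this step and the labelling are all that can still be done.

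The cost is one VAS line at a visit where questionnaires are already completed, plus an amendment. The downsides are two baseline definitions across subjects, a second reading for only the later ones, and a slightly less favourable rate.

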#### **B.6.4. BASELINE**

A subject that is eligible to continue into the trial phase according to the inclusion and exclusion criteria will be requested to fill out standard questionnaires that will assess extent of disability and use of medications. The medical and surgical history of the subject will also be collected. At this visit and subsequent visits, the subject will be assessed for study-related adverse events, medication usage and will be reminded to not increase pain medications from baseline through the 3-Month Visit. Pre-operative assessments will follow the standard of care for SCS therapy and be determined by the site Investigator.

#### **B.6.5. SCS TRIAL PHASE**

Subjects will undergo a Trial Phase with DTM SCS programming. The Trial Phase will last up to 10 days. Percutaneous leads will be placed in the epidural space at a vertebral level based on the subject's pain condition and pain pattern as described in the Physician Implant Manuals. Stimulation will be delivered from an external neurostimulator (ENS).

Anterior-posterior (AP) and lateral X-ray imaging will be done following lead placement at the beginning of the Trial Phase. The subject should flex forward prior to the final AP and lateral X-ray imaging. Additional Imaging may be required if lead migration is suspected throughout the trial.

Stimulation therapy will be as follows:

- Subjects will be given multiple program groups to try. Each DTM SCS program group will have multiple parameters. The stimulation parameters will be within the specifications described in the Intellis™ manuals. Each DTM SCS program group has at least two programs with different pulse rate in the 50 to 1,000 Hz range and each having a maximum pulse width of 1 ms. The subject will progress through each of the program groups until satisfactory pain relief has been reached. The subject will be able to adjust the intensity of the stimulation as deemed needed to obtain pain relief. If sufficient pain relief is not achieved with the initial program group, the subject will be instructed to trial another DTM SCS program group.

Following the standard of care of SCS, adjustments to a program group may be made based on patient feedback following the trialing of a particular program group or set of stimulation parameters. The primary factor for assessing response to a given program group or stimulation parameters is the subject's self-reported pain relief. Adjustments to therapy will be attempted until at least 40% self-reported pain reduction from baseline is achieved or until conclusion of the trial phase (no more than 10 days). Subjects will be assessed for study-related adverse events and medication usage during the duration of the Trial Phase.

### **B.6.6. END OF TRIAL ASSESSMENT**

At the end of the Trial Phase, subjects will be assessed for pain intensity under optimal therapy parameters. Anterior-posterior (AP) and lateral X-ray imaging may be done at the end of the Trial Phase. The subject will be assessed for study-related adverse events and medication usage.

Subjects who have a "successful Trial Phase" (defined as a 40% or greater pain reduction from Baseline in the upper limbs pain and the subject would like to move forward to the implant phase) will proceed to permanent implantation of a SCS system to evaluate DTM SCS programming. Permanent implantation of the Intellis™ SCS system will be scheduled. A threshold of 40% for the Trial Phase was predetermined as the minimum pain reduction that warrants consideration of a permanent implant and an opportunity to achieve a 50% pain reduction as defined in the Individual Subject Success criterion (see Section B.7.3).

Subjects who did not achieve 40% or greater pain reduction in upper limb and do not receive permanent implantation will exit the study after being followed up for two weeks after removal of the leads to assess study-related adverse events.

### **B.6.7. PERMANENT DEVICE IMPLANT (0-60 DAYS FROM END OF SUCCESSFUL TRIAL PHASE)**

As described in section B.6.6, subjects who underwent a successful trial of DTM SCS therapy and who agreed to continue into the next stage of the study will proceed to permanent implantation stage.

Permanent percutaneous leads will be placed in the epidural space at a vertebral level based on the subject's pain condition and pain pattern as described in the Physician Implant Manuals. The implantable neurostimulator (INS) will be implanted by a trained physician according to standard practice and following the Physician Implant Manual for the device. Anterior-posterior (AP) and lateral X-ray imaging will be obtained. The standard practice of the study site will be followed for prophylactic pre-surgery antibiotics. Subjects will be assessed for study-related adverse events and medication usage.

### **B.6.8. DEVICE ACTIVATION (0-14 DAYS FOLLOWING PERMANENT IMPLANT)**

Clinical personnel at the site will assess if healing of surgical wounds is sufficiently appropriate to start charging the INS. The INS will be initially programmed to the group therapy or set of stimulation parameters that provided adequate pain relief during the Trial Phase. Adjustments to therapy may be made based on patient response to a program group or set of stimulation parameters. The subject will be provided with instructions on how to operate the charger and patient remote control at this visit. Subjects will be assessed for study-related adverse events and medication usage.

